#### 10.4. Search Criteria for TEAE of Special Interest/TEAE Syndrome

AESI	Search Criteria
Anaphylactic reactions	
For SMQ “anaphylactic reaction” An algorithmic approach will be used. A case must include either:
 
 
1. A narrow term (a term from Category A);
 
2. Patient with both a term from Category B AND a term from Category C;
 
3. Patient with a term from Category D AND { a term from Category B - OR a term from Category C }
 
 
For bullets 2 and 3, the search terms that are included under the SMQ for a particular event need to have the same start date (for e.g. if search shows cough (category B term) occurring at day 3 and urticaria (category C term) occurring at day 7, this event is not adjudicated as anaphylactic reaction as this is inconsistent with the clinical presentation of anaphylaxis as an acute event with simultaneous involvement of 2 or more body systems.
 
Note: manual adjudication of relevant PTs will be required by the study medical monitor, before database lock

Systemic or severe hypersensitivity reactions	
Hypersensitivity: Narrow SMQ for hypersensitivity excluding preferred term equal to dermatitis atopic or eczema
 
For systemic hypersensitivity, events in which 2 or more body systems are involved (as defined by System Organ Class) would be considered for adjudication based on further medical judgement
 
For severe hypersensitivity, an additional search will be done;
 
 
- HLT = Injection site reactions
 
- Severity = “severe”
 
 
Note: manual adjudication of relevant PTs will be required by the study medical monitor, before database lock

Malignancy	
 
• SMQ “Malignant tumours”
 
• SMQ “Tumours of unspecified malignancy”
 

Helminthic infections 	
 
-HLT = Cestode infections
 
-HLT = Helminthic infections NEC
 
-HLT = Nematode infections
 
-HLT = Trematode infection
 

Suicidal behavior	
Include the following PTs
 
 
• Completed suicide
 
• Suicidal ideation
 
• Suicide attempt
 
• Depression suicidal
 

	
 
• Suicidal behavior
 


Any type of conjunctivitis or blepharitis (severe or serious)
	
broad CMQ conjunctivitis (Conjunctivitis, Conjunctivitis allergic, Conjunctivitis bacterial, Conjunctivitis viral, Atopic keratoconjunctivitis, Blepharitis, Dry eye, Eye irritation, Eye pruritus, Lacrimation increased, Eye discharge, Foreign body sensation in eyes, Photophobia, Ocular hyperaemia, Conjunctival hyperaemia, Xerophthalmia)
 
Blepharitis PTs (Blepharitis, blepharitis allergic)
 
AND
 
Serious AE= “Yes” OR Severity= “severe”
 
Note: manual adjudication of relevant PTs will be required by the study medical monitor, before database lock.

Keratitis
	
Any of the following PTs:
 
 
a. Keratitis
 
b. Allergic keratitis
 
c. Ulcerative keratitis
 
d. Atopic keratoconjunctivitis
 
e. Herpes ophthalmic
 
f. – Ophthalmic herpes simplex
 
 
Note: manual adjudication of relevant PTs will be required by the study medical monitor, before database lock.

 The search criteria are meant to assist the process of identification of TEAE of Special Interest/TEAE Syndrome. However, since these criteria might not be exhaustive in some cases or may not be specific in other cases. Hence an additional blinded review of all PTs in the database may be performed by the Medical monitor, based on medical judgement, to identify any TEAE of Special Interest/TEAE Syndrome that might have been missed by the criteria or to identify any TEAE may been inaccurately assigned as AESI by the algorithmic search

## 10.5. Algorithm for RESCUE TREATMENTS

### 1. Not required to adjudicate rescue treatment:

Post-baseline medications (WHODD-coded) given for indications consistent with AD.

#### a. Always considered rescue:

- ATC2 = CORTICOSTEROIDS FOR SYSTEMIC USE
- ATC2 = IMMUNOSUPPRESSANTS
- Preferred Drug Name = Ciclosporin
- Preferred Drug Name = Methotrexate
- Preferred Drug Name = Mycophenolate sodium
- Preferred Drug Name = Mycophenolic acid
- Preferred Drug Name = Mycophenolate mofetil
- Preferred Drug Name = Azathioprine
- Preferred Drug Name = Crisaborole, if used after day 29
- ATC2 = CORTICOSTEROIDS, DERMATOLOGICAL PREPARATIONS, if used after day 29
- Preferred Drug Name = Tacrolimus, if used after day 29
- Preferred Drug Name = Pimecrolimus, if used day 29

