## **5.3. Rescue Treatment**

If medically necessary (ie, to control intolerable AD symptoms), rescue treatment for AD may be provided to study patients at the discretion of the investigator. If possible, investigators are encouraged to consider rescue initially with topical treatment (eg, medium/high potency TCS) and to escalate to systemic medications only for patients who do not respond adequately after at least 7 days of topical treatment. Topical calcineurin inhibitors may be used for rescue, alone or in combination with TCS, but the use of TCIs should be reserved for problem areas only (eg, face, neck, intertriginous and genital areas, etc.). Investigators may also consider rescue with crisaborole. Rescue treatment for these topical therapies should be used as per prescribing information and local guidelines. Patients may continue study treatment if rescue consists of topical medications.

Patients who receive systemic corticosteroids or systemic nonsteroidal immunosuppressive drugs (eg, cyclosporine, methotrexate, mycophenolate-mofetil, azathioprine, etc) as rescue medication during the study will be discontinued permanently from the study drug. All patients will be asked to complete the scheduled study visits and assessments whether or not they complete study treatment and whether or not they receive rescue treatment for AD. Investigators should make every attempt to conduct efficacy and safety assessments (eg, disease severity scores, safety laboratory tests) immediately before administering any rescue treatment. An unscheduled visit may be used for this purpose, if necessary. For the purpose of efficacy analysis, patients who receive rescue treatment during the study will be considered treatment failures.

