(i.e., both medications and procedures): If medically necessary (i.e., to control intolerable AD symptoms), rescue treatment for AD may be provided to study patients at the discretion of the investigator. For the purpose of efficacy analysis, patients who receive rescue treatment during the study will be considered treatment failures. If possible, investigators are encouraged to consider rescue initially with topical treatment (eg, medium/high potency TCS) and to escalate to systemic medications only for patients who do not respond adequately after at least 7 days of topical treatment. Topical calcineurin inhibitors may be used for rescue, alone or in combination with TCS, but the use of TCIs should be reserved for problem areas only (eg, face, neck, intertriginous and genital areas, etc.). Patients who receive systemic corticosteroids or systemic non-steroidal immunosuppressive drugs (eg, cyclosporine, methotrexate, mycophenolate-mofetil, azathioprine, etc.) as rescue treatment during the study will be discontinued permanently from the study drug. All patients will be asked to complete the scheduled study visits and assessments whether or not they complete study treatment and whether or not they receive rescue treatment for AD. Investigators should make every attempt to

conduct efficacy and safety assessments (eg, disease severity scores, safety laboratory tests) immediately before administering any rescue treatment. An unscheduled visit may be used for this purpose, if necessary.

Blinded adjudication of rescue treatments will be implemented before database locks by considering the type of medication or procedure, indication, timing, frequency and the potential impact of the use of the prohibited medication or procedure. The rescue treatments will be adjudicated by the clinical study director and the adjudication procedure will be documented.

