#### Handling of dropouts or adjudicated rescue treatment or missing value for the binary response variables as the primary analysis

- If a patient withdraws from the study, this patient will be counted as a non-responder for the time points after withdrawal.
- To account for the impact of rescue treatment on the efficacy effect: if rescue treatment is used (see Section 4.3 for rescue treatment), the patient will be specified as a non-responder from the time the rescue treatment is used.
- If the patient has the missing value at week 16, then it will be counted as a non-responder at week 16.

The Mantel-Fleiss (MF) criterion will be performed, and if it is not met while using the option CMH (MF) in SAS procedure PROC PREQ, sensitivity analyses including each factor separately in CMH test will be conducted.

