#### **5.7.2. Analyses of Secondary Efficacy Variables**

The binary secondary efficacy endpoints will be analyzed using the same approaches as that are used for the analysis of the primary endpoints.

The endpoint "Proportion of patients with improvement (reduction) of weekly average of daily peak pruritus NRS  $\geq 4$  from baseline to week 16" will only be analyzed for patients with baseline peak pruritus NRS  $\geq 4$ . Similarly the endpoint "Proportion of patients with improvement (reduction) of weekly average of daily peak pruritus NRS  $\geq 3$  from baseline to week 16" will only be analyzed for patients with baseline peak pruritus NRS  $\geq 3$ .

The continuous endpoints will be analyzed using the multiple imputation (MI) with analysis of covariance (ANCOVA) model as the primary analysis method. Patients' efficacy data through week 16 after the rescue treatment use will be set to missing first, and then be imputed by the multiple imputation method. Missing data from the FAS will be imputed 40 times to generate 40 complete data sets by using the SAS procedure MI following the 2 steps below:

- Step 1: The monotone missing pattern is induced by Markov Chain Monte Carlo (MCMC) method in MI procedure. The monotone missing pattern means that if a patient has missing value for a variable at a visit, then the values at all subsequent visits for the same variable are all missing for the patient.
- Step 2: The missing data at subsequent visits will be imputed using the regression method for the monotone pattern with adjustment for covariates including treatment groups, randomization strata (disease severity, age group), and relevant baseline.

The week 16 data of each of the 40 complete datasets will be analyzed using an analysis of covariance (ANCOVA) model with treatment, randomization strata (disease severity, age group), and relevant baseline included in the model, and the SAS MIANALYZE procedure will be used to generate valid statistical inferences by combining results from the 40 analyses using Rubin's formula.

The imputation model will include:

- The covariates included in the ANCOVA model, including the treatment group, the baseline value and the randomization strata (disease severity, weight group)
- Measured endpoint values at every clinic visit (i.e. week 1, 2, 3, 4, 8, 12 and week 16)

Categorical variables included in above model (i.e., treatment group and randomization strata) are not expected to be missing.

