#### b. Never considered rescue:

- ATC2 = EMOLLIENTS AND PROTECTIVES
- ATC2 = VASOPROTECTIVES
- ATC2 = ANALGESICS
- ATC2 = ANTI-ACNE PREPARATIONS
- ATC2 = TOPICAL PRODUCTS FOR JOINT AND MUSCULAR PAIN
- ATC2 = ANTIBIOTICS AND CHEMOTHERAPEUTICS FOR DERMATOLOGICAL USE
- ATC2 = ANTIVIRALS FOR SYSTEMIC USE
- ATC2 = ANTIFUNGALS FOR DERMATOLOGICAL USE
- ATC2 = ANTISEPTICS AND DISINFECTANTS
- ATC2 = ANTIHISTAMINES FOR SYSTEMIC USE
- ATC2 = ANTIPRURITICS, INCL. ANTIHISTAMINES, ANESTHETICS, ETC.
- ATC2 = GENERAL NUTRIENTS
- ATC2 = VITAMINS

 A blinded review of all post-baseline medications to adjudicate rescue treatment, based on medical judgement, may be performed in addition. A listing of treatments classified as rescue/non-rescue in a manner inconsistent with the classification under #1 will be provided, along with supporting rationale.

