**2. Require to adjudicate rescue treatment:**

- All other medications (not noted in #1 above) given for indications consistent with AD
- Medications noted in 1a above, when given for indications not consistent with AD

 Below is a list of indications consistent with AD based on PT level from concomitant medication/procedure data using MedDRA dictionary

System Organ Class	High Level Term	Preferred Term	Preferred Term Code
Infections and infestations	Bacterial infections NEC	Eczema impetiginous	10051890
Infections and infestations	Skin structures and soft tissue infections	Dermatitis infected	10012470
Infections and infestations	Skin structures and soft tissue infections	Eczema infected	10014199
Skin and subcutaneous tissue disorders	Dermatitis and eczema	Dermatitis	10012431
Skin and subcutaneous tissue disorders	Dermatitis and eczema	Dermatitis atopic	10012438
Skin and subcutaneous tissue disorders	Dermatitis and eczema	Eczema	10014184
Skin and subcutaneous tissue disorders	Dermatitis and eczema	Neurodermatitis	10029263

Signature Page for VV-RIM-00043851 v1.0

Approval	[Redacted]
----------	------------

Approval	[Redacted]
----------	------------

Approval	[Redacted]
----------	------------

Signature Page for VV-RIM-00043851 v1.0 Approved

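### Time to onset of itch relief has no rescue rule of its own in SAP 5.7.2, so relief after rescue counts as onset if the text is followed literally; the pimecrolimus line in SAP 10.5 also needs correcting

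*SAP*

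**What the plan says.** **Failure principle.** Protocol 5.3 states: "For the purpose of efficacy analysis, patients who receive rescue treatment during the study will be considered treatment failures". SAP 4.3 repeats the sentence. Neither sets a day limit.

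**Endpoint rules.** SAP 5.7.1 makes a rescued patient a non-responder from the time of rescue, under the heading "Handling of dropouts or adjudicated rescue treatment or missing value for the binary response variables as the primary analysis". SAP 5.7.2 extends this to other binary endpoints: "The binary secondary efficacy endpoints will be analyzed using the same approaches as that are used for the analysis of the primary endpoints". For continuous endpoints, SAP 5.7.2 sets data after rescue to missing.

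**Time to onset.** The paragraph in SAP 5.7.2 takes the date of the first event minus the first dose date plus one day, censors patients without an event at the end of the treatment period, and fits a Cox model with treatment and strata. Rescue is not mentioned. The formula is given only for the 4-point version, but the hierarchy tests the 3-point version too (ranks 17 and 25, against 18 and 26 for 4 points).

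**Rescue classification.** In SAP 10.5, item 1a, systemic corticosteroids and immunosuppressants given for AD are automatic rescue with no day limit. Topical corticosteroids are listed as "ATC2 = CORTICOSTEROIDS, DERMATOLOGICAL PREPARATIONS, if used after day 29", and tacrolimus and crisaborole carry the same condition. Pimecrolimus reads "Preferred Drug Name = Pimecrolimus, if used day 29". Item 2 sends to adjudication "All other medications (not noted in #1 above) given for indications consistent with AD". A footnote adds: "A blinded review of all post-baseline medications to adjudicate rescue treatment, based on medical judgement, may be performed in addition". SAP 4.3 names the adjudicator: "The rescue treatments will be adjudicated by the clinical study director and the adjudication procedure will be documented".

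**The concern.** The time-to-onset tests sit inside the alpha-controlled hierarchy. A programmer who codes the paragraph as written would credit the randomised arm with itch relief that follows rescue. The same patient would be a non-responder in the binary analysis of the same diary scores. The tests at ranks 17 and 18 also gate everything after them, so a loss there ends formal testing of ranks 19 to 40.

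The pimecrolimus line, coded literally, applies to a single day. Two topical calcineurin inhibitors given for AD after day 29 would then take different routes: tacrolimus automatic, pimecrolimus adjudicated.

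For topical use that ended by day 29, rescue status depends on adjudication. This matters most for the week-4 pruritus tests (ranks 24, 32, 34 and 36), and no planned analysis shows the result if all such use counts as rescue.

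**Working it through.** **1. The plan's own figures.** With 80 per arm and a two-sided 5% test, the stated power for the 4-point itch response is 97% (38% vs 11%, Q2W) and 95% (36% vs 11%, Q4W). Fisher's exact test gives 97.7% and 95.9%. For IGA 0 or 1, stated 98% and 88%, it gives 98.9% and 88.1%. The sample size is not in question.

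**2. Which rule reaches which endpoint.**

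| Endpoint type | Rescue rule in SAP 5.7 |
|---|---|
| Binary | Non-responder from time of rescue (5.7.1, extended in 5.7.2) |
| Continuous | Data after rescue set to missing (5.7.2) |
| Time to onset | None stated; censored only at end of treatment |

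**3. Diary windows (SAP 6.4).** Week 1 is days 2 to 8, so week *k* is days 7*k* − 5 to 7*k* + 1. Week 4 is days 23 to 29. For topical use that ended by day 29, the automatic trigger cannot reach the week-4 tests.

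**4. Time to onset, illustration.** Only 80 per arm and the Q2W rates of 38% and 11% come from the plan; those week-16 rates stand in for cumulative onset. Rescue rates and the share *q* of rescued patients who then improve are assumed. Natural onset is uniform over weeks 1 to 16, rescue uniform over weeks 1 to 14, and relief comes two weeks after rescue. Each scenario has 3,000 simulated trials and an unstratified log-rank test. HR = ln(1 − p_drug)/ln(1 − p_placebo); without rescue, ln(0.62)/ln(0.89) = 4.10. Under the rule, rescued patients stay in the risk set but later improvement is not an event.

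| Rescue, placebo/drug | *q* | As written: onset drug vs placebo, HR, power | With rule: onset drug vs placebo, HR, power |
|---|---|---|---|
| 10%/5% | 0.25 | 38.8% vs 13.2%, 3.5, 97% | 37.0% vs 10.4%, 4.2, 98% |
| 30%/15% | 0.40 | 41.6% vs 21.7%, 2.2, 78% | 34.9% vs 9.3%, 4.4, 98% |
| 20%/20% | 0.40 | 43.1% vs 18.0%, 2.9, 95% | 34.2% vs 9.7%, 4.1, 97% |
| 15%/30% | 0.40 | 45.4% vs 16.3%, 3.4, 98% | 32.0% vs 10.1%, 3.6, 94% |

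The literal reading dilutes the HR in all four cases. Power falls in three and rises in the fourth.

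**5. Week-4 binary test, illustration.** Observed rate = (1 − r)b + r(1 − a)[b + (1 − b)q]. Here r is early topical use, a the share of early users judged rescue, and b the response without topical effect (assumed 20% drug, 6% placebo). Power is the two-proportion normal approximation, 80 per arm; with no early use it is 75%.

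| Early use, placebo/drug | *q* | Power if none / half / all judged rescue |
|---|---|---|
| 20%/10% | 0.40 | 35 / 53 / 75% |
| 20%/20% | 0.40 | 53 / 57 / 64% |
| 10%/20% | 0.40 | 79 / 69 / 58% |
| 5%/5% | 0.25 | 71 / 72 / 73% |

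**6. The two extremes do not bracket the treatment difference.** Take 20%/20% use, *q* = 0.40. An unflagged early user responds with probability 0.20 + 0.80 × 0.40 = 0.52 on drug and 0.06 + 0.94 × 0.40 = 0.436 on placebo. If 40% of drug and 60% of placebo early users are judged rescue:

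- drug: 0.80 × 0.20 + 0.20 × 0.60 × 0.52 = 0.222
- placebo: 0.80 × 0.06 + 0.20 × 0.40 × 0.436 = 0.083

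Power is 69%. With the shares reversed, the rates are 0.202 and 0.100 and power is 43%. Both fall outside the 53 to 64% between the extremes.

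**7. Primary test, tipping point.** Planned responders are about 23/80 (Q4W), 30/80 (Q2W) and 7/80 (placebo). Pearson chi-square against 7/80 gives p = 0.0012 for 23/80, 0.043 for 16/80 and 0.066 for 15/80. With placebo fixed, 8 of 23 Q4W or 15 of 30 Q2W responders would have to change status before p exceeds 0.05.

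**The case against.** The strongest reply is that the intent is already clear. SAP 4.3 states the failure principle for efficacy analysis in general. SAP 4.4.2 and 5.7.2 describe time to onset through the proportion of patients with improvement, which is a binary response, and weekly itch scores after rescue are set to missing in the continuous analyses. That largely stands as to intent. It does not complete the algorithm: the Cox paragraph never applies the principle, and the principle does not say whether a rescued patient stays at risk without an event or is censored, or what becomes of an onset before rescue.

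It is also fair that the pimecrolimus line is evidently a slip, since the three other topical lines carry the condition. Read literally, later use still goes to adjudication and is not declared non-rescue.

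A reader might infer that the day-29 limit excuses early topical use. The documents do not support that. The limit governs automatic classification only, such use is not on the never-rescue list, and adjudication is blinded, precedes database lock, weighs stated factors and is documented. Any classification that departs from item 1 must be listed with its rationale. One wording gap remains: item 2 covers medications not noted in item 1, and these drugs are named there, so adjudication is the natural reading but not an explicit one.

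Nor is it right that nothing planned tests the dependence on adjudication. The all-observed analyses reach the week-4 itch endpoints and show the lenient end. Only the strict end is missing, and for time to onset no all-observed run is planned.

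**Conclusion.** The point holds as a gap in specification. Followed literally, SAP 5.7.2 counts itch improvement after rescue as onset at ranks 18 and 26, and at ranks 17 and 25 if the same formula is used for 3 points. That is contrary to the failure principle in Protocol 5.3 and SAP 4.3. The pimecrolimus line is an operative line that needs correcting. Early topical use has a legitimate route, so a strict sensitivity analysis is a cheap addition there and not the correction of an error.

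Size and direction are unknown. The documents give no rescue or early-use rates, and every HR and power figure for time to onset and week 4 rests on assumed ones. A reader might infer from the steepest scenarios that the drug effect would be overstated or that the main result is at risk. Neither is supported: the literal reading diluted the HR in every scenario tried, power moved both ways, the affected tests cannot block ranks 1 to 16, and the primary test is fairly robust.

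**What to change.** Analysis only, before database lock; no clinical rescue rule is proposed.

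1. In SAP 5.7.2, state for both the 3-point and 4-point versions that improvement after rescue is not an onset event, and how the follow-up time of rescued patients is handled, consistent with the non-responder rule in 5.7.1.
2. In SAP 10.5, give the pimecrolimus line the same analysis condition as the other topical agents, and state in item 2 that topical use for AD through day 29 is adjudicated.
3. Add one sensitivity analysis that counts all post-baseline topical corticosteroids, topical calcineurin inhibitors and crisaborole given for AD as rescue from first use, for the week-4, week-16 and time-to-onset endpoints. Describe it as the strict extreme for each arm's rate, not as one end of a bracket around the treatment difference. For time to onset, run the all-observed version as well.

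Cost: a short rule, two corrections and two extra runs on data already collected. In the strict run some early topical users become non-responders or missing.

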#### b. Never considered rescue:

- ATC2 = EMOLLIENTS AND PROTECTIVES
- ATC2 = VASOPROTECTIVES
- ATC2 = ANALGESICS
- ATC2 = ANTI-ACNE PREPARATIONS
- ATC2 = TOPICAL PRODUCTS FOR JOINT AND MUSCULAR PAIN
- ATC2 = ANTIBIOTICS AND CHEMOTHERAPEUTICS FOR DERMATOLOGICAL USE
- ATC2 = ANTIVIRALS FOR SYSTEMIC USE
- ATC2 = ANTIFUNGALS FOR DERMATOLOGICAL USE
- ATC2 = ANTISEPTICS AND DISINFECTANTS
- ATC2 = ANTIHISTAMINES FOR SYSTEMIC USE
- ATC2 = ANTIPRURITICS, INCL. ANTIHISTAMINES, ANESTHETICS, ETC.
- ATC2 = GENERAL NUTRIENTS
- ATC2 = VITAMINS

 A blinded review of all post-baseline medications to adjudicate rescue treatment, based on medical judgement, may be performed in addition. A listing of treatments classified as rescue/non-rescue in a manner inconsistent with the classification under #1 will be provided, along with supporting rationale.

